	
Evaluation of Safety:
 
Adverse Events (AEs) will be obtained from signs and symptoms reported by the subject or detected during each examination visit to obtain information about any medical occurrence that meets the definition of an AE.
 
[REDACTED]
 
[REDACTED]
 
[REDACTED]
 
Any subject with a treatment related AE that is ongoing at the time of study completion will be followed until that AE is resolved or stabilized. Any AE assessed as related to the study product or injection procedure with onset after subject participation in the study is over, and that the Investigator becomes aware of should be reported to the Sponsor.
 
All subjects will complete a Diary for 28 days after each treatment, to collect information about pre-defined, expected, post-treatment events at the treated area..
 
[REDACTED]
 
[REDACTED]
 
[REDACTED]

Study Procedures	
Study Report
 
A study report will be compiled at the conclusion of the study. This report will be included in the regulatory submission for marketing application.

Schedule of Events	
 • [REDACTED] – [REDACTED] – [REDACTED] – [REDACTED]

Effective date: 2019-02-21 18:33

Effective

Version: 5.0

	• [REDACTED]	[REDACTED]
	• [REDACTED]	[REDACTED]
	• [REDACTED]	[REDACTED]
Effectiveness assessments	• [REDACTED]	[REDACTED]
	• [REDACTED]	[REDACTED]
Safety Assessments	• [REDACTED]	[REDACTED]
	• [REDACTED]	[REDACTED]
Statistical Methods	[REDACTED]	[REDACTED]
	[REDACTED]	[REDACTED]

Effective

Effective date: 2019-02-21 18:33

Version: 5.0

Principles for the analysis

All results will be evaluated for the treatment group and reference group separately.

Effective date: 2019-02-21 18:33

Effective

Version: 5.0

 GALDERMA	Title 43USSA1705 Sculptra Clinical Study Protocol	Doc id MA-37876
--	---	---------------------------

Abbreviations and Definitions of Terms

AE	Adverse event
AESI	Adverse event of special interest
Blinded Evaluator	An evaluator responsible for independent evaluation of treatment result(s). The evaluator must not be involved in the treatment of the subject.
CE	French: Conformité Européenne
CFR	Code of Federal Regulations

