5.5 Withdrawal of subjects

Each subject shall be advised in the informed consent form that the subject has the right to withdraw from the study at any time, for any reason, without prejudice. Subjects may also be discontinued from this study if the Investigator determines that it is in the subject's best interest to do so, and may be withdrawn at the Investigator's discretion at any time.

[REDACTED]

[REDACTED]

[REDACTED]

[REDACTED]

[REDACTED]

[REDACTED]

[REDACTED]

[REDACTED]

[REDACTED]

The reason and date for withdrawal shall be documented in the eCRF. When possible, an explanatory comment shall be added to further explain the reason for withdrawal. If withdrawal of a subject occurs during a regular study visit, the eCRF for that specific visit shall be completed as far as possible.

 GALDERMA	Title 43USSA1705 Sculptra Clinical Study Protocol	Doc id MA-37876
--	--	----------------------------------

If withdrawal of a subject occurs between regular study visits, the subject should when possible (irrespective of the reason for withdrawal) be scheduled for a termination visit to document subject outcome for the secondary endpoints.

If a subject is withdrawn from the study, all data collected until the time of withdrawal will be used in the analyses.

Subjects who receive product and are withdrawn or discontinued from the study will not be replaced.

For AEs still ongoing at the time of withdrawal, see Section 7.7.8.

6. Study Products

The term “study product” refers to Sculptra Aesthetic (i.e. the investigational product and the reference product). The study product will be provided by the sponsor.

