7.7.3 Recording instructions

Each subject with an AE occurring after enrollment through study exit should be fully recorded in the source document(s) for further transcription to the eCRF. Each subject should be questioned about AEs at each study visit following randomization and or treatment. The question asked should be: "Since your last clinical visit have you had any health problems?" Information on AEs can also be obtained from signs and symptoms detected during each examination.

⁷ For users or other persons, this definition is restricted to events related to the investigational product.

⁸ The term "life threatening" in the definition of "serious" refers to an event in which the patient was at risk of death at the time of the event; it does not refer to an event which hypothetically might have caused death if it were more severe. (Source: ICH E2A clinical safety data management: definitions and standards for expedited reporting).

⁹ Planned hospitalization for a pre existing condition, or a procedure required by the CSP, without serious deterioration in health, is not considered a SAE. (Source: ISO14155:2011).

	Title 43USSA1705 Sculptra Clinical Study Protocol	Doc id MA-37876
--	---	---------------------------

Effective date: 2019-02-21 18:33

Effective

Version: 5.0

Exceptions from AE reporting are normal fluctuations in pre-existing diseases. However, pre-existing illnesses that deteriorates (in intensity or frequency) shall be reported as AEs.

When an AE is related to a device deficiency (refer to section 7.8), including technical device malfunction, the AE shall be recorded on the AE form in the eCRF and the technical complaint shall be reported separately on the clinical study complaint form.

Investigators, or other study site personnel, shall record all AEs in the eCRF, including:

- a) Event term (recorded in standard medical terminology and avoiding abbreviations)
- b) Description of event and affected area
- c) Start date (first day with symptoms)
- d) Stop date (last day with symptoms)
- e) Intensity (mild, moderate, or severe according to definition in Section 7.7.3.1)
- f) Seriousness (serious or not serious, according to definition in Section 7.7.3.2)
- g) Causal relationship to study product or study product injection procedure (yes or no)
- h) Action taken (none, medication treatment, non-medication treatment, or other procedures/tests, subject withdrawn)

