- i) Outcome of the AE (ongoing, recovered, recovered with sequelae, death, chronic/stable, not recovered at the end of the study)

The pre-defined, expected post-treatment events shall be assessed separately. These event shall be collected daily by subjects in a Diary for up to 28 days after each treatment.

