#### 1.6 Safety Endpoints

Safety endpoints include:

- Incidence, intensity, time to onset, and duration of adverse events collected throughout the study period.
- Incidence, intensity, time to onset and number of days of pre-defined expected post-treatment events collected using subject diaries for 28 days from each treatment.
- [REDACTED]  
[REDACTED]

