### 2.1.2 Reporting Conventions

The formats for the tables, listings, and figures described in this SAP will be provided in a companion document. Changes to the formats of these reports that are decided after the finalization of the SAP will not require an amendment. In addition, any additional supportive or exploratory analyses requested after SAP approval will not require amendment of the SAP. These additional analyses will be described in the CSR.

All study data from the eCRFs as well as derived variables will be provided in subject data listings. An indication of specific listings for each data type will not be indicated in the text of subsequent SAP sections. Data listings supplied as part of the CSR will be sorted by study center number concatenated with subject number, assessment dates, and/or time point.

The following conventions will be applied to all data presentations and analyses:

- Quantitative variables will generally be summarized by the number of subjects, mean, standard deviation, median, minimum, and maximum. Unless otherwise specified, the minimum and maximum values will be displayed to the same number of decimal places as the raw data, the mean and median will be presented to one extra decimal place compared to the raw data, and the standard deviation will be displayed to two extra decimal places compared to the raw data
- Categorical variables will be summarized by the number and percentage of subjects (and number of events where appropriate) within each category. Unless otherwise specified, the percentage will be presented in parentheses to one decimal place. Frequency and percentage values of 0 will be presented as '0' rather than '0 (0)'.
- All summary tables will include the analysis population sample size (i.e. number of subjects).
- Date variables will be formatted as ddMMYY YYYY for presentation.

 GALDERMA	Title Statistical Analysis Plan 43USSA1705 - New label	Doc id MA-39345
--	--	---------------------------

2.1.3 [REDACTED]

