## 2.5.2 Adverse Events

A summary of all AEs (number and percentage of subjects with at least one event and number of events) will be provided, which will include:

- Subjects with at least one AE (in total as well as serious AEs).
- Subjects with at least one study product or injection procedure-related AE (in total as well as serious AEs).
- Subjects with at least one unrelated AE (in total as well as serious AEs).
- Subjects with at least one AE of special interest (in total as well as serious AEs).
- Number of subjects who did not have an AE.

As a sensitivity analysis, the above will be repeated using only randomized subjects.

Apart from the summary table described above, all other adverse event tables will be summarized in total and by treatment session: the first treatment session will include all AEs with a date of onset on or after the first treatment date but before the date of the second treatment or through the end of the trial if a subject receives only one treatment; the second treatment session will include all AEs with a date of onset on or after the second treatment date but before the date of the third treatment or through the end of the trial if a subject receives only two treatments, etc.

Study product or injection procedure-related AEs, as well as AEs unrelated to study product or injection procedure will be summarized by System Organ Class (SOC), Preferred Term (PT) and maximum intensity.

In addition, for study product or injection procedure-related AEs, the number of days to onset and the duration of event will be summarized by SOC and PT.

- Time to onset of an AE will be derived as the start date minus the date of the most recent treatment. If the start date is missing, it will be assumed that the AE started on the day of the most recent treatment.
- Duration of an AE will be derived as the stop date minus the start date + 1. If the start date is missing, it will be assumed that the AE started on the day of most recent treatment. Missing stop dates will not be imputed and therefore no duration will be calculated in these cases.

Actions taken for study product or injection procedure-related AEs will also be summarized.

Serious AEs, AEs of special interest, and AEs with late onset (i.e. AEs with onset > 21 days after most recent treatment) will be listed.

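### The adverse event duration summary in SAP 2.5.2 covers resolved related events only, and no visible text ties the number left out to that table (minor)

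*SAP*

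**What the plan says.** SAP 1.6 lists the endpoint: "Incidence, intensity, time to onset, and duration of adverse events collected throughout the study period". SAP 2.5.2 states that, for AEs related to the product or the injection procedure, "the number of days to onset and the duration of event will be summarized by SOC and PT". Duration is stop date minus start date plus one. A missing start date is replaced by the day of the most recent treatment, but for the other end of the interval: "Missing stop dates will not be imputed and therefore no duration will be calculated in these cases".

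Protocol 7.7.3 defines what is recorded: "Stop date (last day with symptoms"), and "Outcome of the AE (ongoing, recovered, recovered with sequelae, death, chronic/stable, not recovered at the end of the study"). The Protocol Synopsis (Evaluation of Safety) says that a treatment-related "AE that is ongoing at the time of study completion will be followed until that AE is resolved or stabilized". Protocol 5.5 adds: "For AEs still ongoing at the time of withdrawal, see Section 7.7.8". Section 7.7.8 is not visible in the public text.

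On reporting, SAP 2.1.2 says: "Quantitative variables will generally be summarized by the number of subjects, mean, standard deviation, median, minimum, and maximum". It also promises subject listings of all eCRF data and derived variables, and leaves table formats to a companion document. SAP 2.5 makes all safety summaries descriptive, by treatment group, on observed cases.

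**The concern.** Whether an event has a duration depends on whether it has ended. Events that last longest are the most likely to be open when the data are locked, so dropping open events removes durations selectively from the long end. This is right-censoring handled by deletion.

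What is at stake is how the duration table is read. Persistent reactions are the ones for which duration is most informative and for which the table would be least complete. Safety is judged descriptively, with the 8 mL and 5 mL groups summarised separately. If the unresolved share differed between groups, a side-by-side reading of durations could mislead, and nothing on the face of the table would say so.

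**Working it through.** **No figure to reproduce.** The documents state no expected AE duration and no expected share of unresolved AEs. The check is one of logic, then of size under stated assumptions.

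**1. Which events get a duration.** Set the SAP 2.5.2 rule against the outcome list in Protocol 7.7.3:

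- Recovered, stop date known: duration computed.
- Recovered, stop date unknown: no duration.
- Ongoing, chronic/stable, or not recovered at study end: symptoms have no last day, so we infer no stop date and no duration.

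The last line is an inference, because no eCRF completion rule is visible. The second and third lines are different kinds of missing value, and the rule treats them alike.

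**2. Direction.** Let D be the duration of an event and C the time from its onset to last contact. Only events with D ≤ C are summarised. If C is independent of D, then E[D | D ≤ C] ≤ E[D]. On average the summary cannot lean long; it leans short whenever some events are open.

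**3. Bound that needs no model for the durations.** Suppose a share p of related AEs has no stop date and these are the longest. The reported median is then the 50 × (1 − p)th percentile of all related AEs:

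- p = 5%: 50 × 0.95 = 47.5th
- p = 10%: 50 × 0.90 = 45th
- p = 25%: 50 × 0.75 = 37.5th

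**4. Illustration (all inputs assumed).** Durations are exponential with mean m = median / ln 2. Onset is uniform over days 0 to 336 (48 weeks × 7), and the cutoff is day 336. The share still open at cutoff is (m/336) × (1 − e^(−336/m)). For a true median of 60 days, m = 60/0.693 = 86.6, and the share is 0.2576 × 0.9794 = 25.2%. Reported medians come from numerical integration of the same model.

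| True median (days) | Open at day 336 | Reported median, no open event later gains a stop date | Half do | All do |
|---|---|---|---|---|
| 14 | 6.0% | 13.1 | 13.6 | 14 |
| 60 | 25.2% | 43.9 | 52.2 | 60 |
| 180 | 56.1% | 72.9 | 130.5 | 180 |

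Other assumed onset windows (days 0–112 and 84–336) keep the 14-day shortfall at about one day or less. The 180-day row has no support in the documents; it shows only how the shortfall grows with duration.

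**5. Why an elapsed time helps.** Take 20 related events, where resolved ones lasted 14 days and unresolved ones have already lasted 180 (assumed). The resolved-only mean is 14 days whatever the number excluded. Counting open events at their elapsed time gives a lower bound for the mean of all 20:

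- 1 open: (19 × 14 + 1 × 180)/20 = 22.3 days
- 2 open: (18 × 14 + 2 × 180)/20 = 30.6 days
- 4 open: (16 × 14 + 4 × 180)/20 = 47.2 days

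**The case against.** The best defence has four parts.

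- **Follow-up.** Related AEs ongoing at study completion are followed until they resolve or stabilise. This stands and shrinks the excluded group, possibly to nothing. It does not cover an event that stabilises while still symptomatic, and the visible text does not say whether stop dates learned after the last visit enter the locked database.
- **Missing values are already to be counted.** Protocol 10.8 has a general sentence on summarising missing values as appropriate, and SAP 2.4.2 repeats it under effectiveness. The Protocol sentence can fairly be read to include stop dates. It does not place the count beside the durations.
- **Open events are visible elsewhere.** SAP 2.1.2 lists all data. SAP 2.5.2 lists serious AEs, AEs of special interest and late-onset AEs, and shows AE tables by treatment session. SAP 2.5.5 summarises nodule and papule assessments. With about 80 subjects, a careful reader could count the open events.
- **Not imputing is ordinary practice** and fits the observed-cases convention. Agreed; the point asks for no imputation.

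A reader might infer that the subject count in the table conceals the problem, since a subject with one resolved and one unresolved event of the same term would still be counted. The documents do not establish this. SAP 2.1.2 says only that subject counts are generally used, duration is defined per event, and by-session tables would separate many repeats.

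Absence can be claimed only for the visible text: SAP 2.5.3, Protocol 7.7.8 and the table shells cannot be seen.

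**Conclusion.** The point holds as a minor reporting matter. The SAP 2.5.2 rule makes the duration summary a summary of resolved related AEs, and it leans short to the extent that unresolved ones exist. This rests on two assumptions: that an unresolved AE has no stop date, and that time to last contact is unrelated to duration.

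The size cannot be derived from the documents. It is zero if all related AEs gain a stop date, about one day or less at a true median of 14 days under the assumed model, and larger only for long-lasting events that are never closed.

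Two stronger readings are not supported. One is that durations will be understated by months: this needs an assumed median near 180 days with little or no later recovery of stop dates, despite the planned follow-up. The other is that the study's success is at risk: the safety criterion in SAP 2.1 has no visible threshold and does not name duration. No hypothesis test, incidence or intensity result changes.

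**What to change.** In SAP 2.5.2:

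1. Label the existing statistics as durations of resolved events.
2. Beside them, by treatment group, SOC and PT, show the number of related AEs (events, not subjects) unresolved at last contact, with their elapsed time or its range.
3. Show separately the number of resolved AEs whose stop date is unknown.
4. Optionally, for pooled related AEs or common terms only, add a descriptive Kaplan-Meier median with unresolved events censored at last contact.

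Items 1 to 3 are the substance. They need a sentence or two of SAP text and a few table columns; start date, stop date and outcome are already collected under Protocol 7.7.3. If the table shells or SAP 2.5.3 already do this, a cross-reference is enough.

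Item 4 has real limits. The median may be inestimable for sparse or long-lasting terms. Repeat events within a subject are not independent, and withdrawal because of a persistent AE would make the censoring informative. It should stay a descriptive point estimate.

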#### 2.5.4 Subject Diary Symptoms

Diary data will be presented for each diary separately. The number and percentage of subjects reporting each pre-defined, expected, post-treatment symptoms, as collected in the 28-day diary, will be presented in total and by maximum severity. Number of days with the event will be presented by treatment group and category: 1, 2-7, 8-14, and 15-28.

#### 2.5.5 Other Safety Analyses

Nodules and papules assessments will be summarized.

Device deficiencies and vision function assessments will be listed.

### 2.6 Interim Analysis

Since the Sponsor is not blinded to treatment in this study, available data may be analyzed prior to study completion.

### 2.7 Determination of Sample Size

In the pivotal study report on which PMA P030050 Supplement 2 was based, [REDACTED] was used for effectiveness assessment. The change from baseline in [REDACTED] at Month 9 post treatment (which should approximately correspond to Week 48 in the current study, in case all four treatments are done) was -0.74 in the Sculptra group and the standard deviation was 0.57. However, the primary effectiveness endpoint was calculated differently in the pivotal study; the median of the left and right averages from three different evaluators was used. Since no averaging or use of the median of different measurements is done in the current study, the standard deviation is expected to be larger than in the pivotal one. Hence a standard deviation of 1 is assumed for these sample size calculations. Furthermore, with an assumed population change from baseline of -0.74, 90% power and one-sided test at the 2.5% significance level, at least 22 subjects are needed. With a drop-out rate of 15% at Week 48, at least 26 will need to be included to the treatment group. However, it was judged that 60 subjects would need to be included to the treatment group in order to provide a reasonable amount of safety data.

For the reference group, the rationale for sample size is based on effectiveness only. With 17 evaluable subjects, the study is adequately powered (80% power using a one-sided test at the 2.5% significance level) to detect a statistically significant change from baseline in [REDACTED] at Week 48, using the same assumptions for standard deviation and change from baseline as for the treatment group. With a drop-out rate of 15% at Week 48, at least 20 subjects need to be included to the reference group.

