## 2 Statistical Methods

### 2.1 General Methods

Any change made to the finalized SAP before database lock will result in a SAP amendment. Otherwise, the change will be documented in the Clinical Study Report (CSR).

Some of the analyses detailed here may be more explicit or in some aspects different from those stated in the protocol. In case of differences, this SAP supersedes the statistical sections in the protocol.

For the study to be deemed successful, the following criteria need to be met:

- The primary effectiveness endpoints (change from baseline in [REDACTED] at Week 48 as assessed by the Blinded Evaluator) should be statistically significantly  $< 0$  on both sides of the face in the treatment group

 GALDERMA	Title Statistical Analysis Plan 43USSA1705 - New label	Doc id MA-39345
--	--	---------------------------

- The confidence intervals around the point estimates of the primary effectiveness endpoints in the treatment group should overlap with those of the reference group
- Acceptable safety profile in the treatment group.

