#### 2.4.2 Handling of Missing Data

The number of missing values will be summarized and reported as appropriate.

For ITT analyses of the primary endpoint, missing values will be imputed using the baseline observation carried forward (BOCF) method. The impact of missing data on the primary endpoint will be evaluated by performing a sensitivity analysis based on the observed cases in the ITT population.

All other effectiveness endpoints will be evaluated based on the observed cases in the ITT population.

[REDACTED], if at least 3 of the scale's 5 items are answered, the sum score to be used in the Rausch transformation will be computed as the mean of the completed items times 5.

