#### 2.4.3 Primary Effectiveness Analysis

For the 8 mL treatment groups the mean change from baseline in [REDACTED] as assessed by the Blinded Evaluator at Week 48 (denoted as  $\mu$ ) will be evaluated using a one-sided Student's t-test. Thus  $H_0: \mu \geq 0$  will be tested against  $H_1: \mu < 0$  in the right and left side of the face separately. In other words; the null hypothesis of no mean change in [REDACTED] (or possibly a worsening) as compared with baseline will be tested against the alternative hypothesis of an improvement from baseline in [REDACTED]. The test will be performed at the 2.5% significance level. Both right and left sides of the face will need to be statistically significantly less than 0 for the treatment to be judged effective. Results will include one-sided p-values and two-sided 95% confidence intervals for the mean change from baseline for both treatment groups. In order to confirm that there are comparable treatment effects in the two groups, there should be an overlap of the confidence intervals. A figure of these confidence intervals will be given.

As a sensitivity analysis, the above will be repeated using only randomized subjects.

Further, separate summaries and analyses will be created for each skin type and for each site. Consistency across skin types and sites will be explored by using an analysis of variance model. Separate models will be run with effects for 1) treatment, skin type, and treatment by skin type interaction, and 2) treatment, site, and treatment by site interaction.

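### Does the 90% power quoted for 22 subjects on 8 mL fall short because both sides of the face must be significant?

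*SAP*

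**What the plan says.** SAP 2.7 builds the 8 mL sample size from three inputs: a mean change ("with an assumed population change from baseline of -0.74"), a spread ("Hence a standard deviation of 1 is assumed for these sample size calculations") and a single one-sided test. The result is "90% power and one-sided test at the 2.5% significance level, at least 22 subjects are needed". It then allows for loss to follow-up: "With a drop-out rate of 15% at Week 48, at least 26 will need to be included to the treatment group". The next sentence moves on from that minimum: "it was judged that 60 subjects would need to be included to the treatment group", for the sake of safety data. Protocol 4.1 also plans about 60 subjects on 8 mL.

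The decision rule stands elsewhere. SAP 2.4.3 tests each side separately at the one-sided 2.5% level and adds: "Both right and left sides of the face will need to be statistically significantly less than 0 for the treatment to be judged effective". SAP 2.1 makes the same demand a condition of study success, "on both sides of the face in the treatment group". For the ITT analysis of the primary endpoint, SAP 2.4.2 says that "missing values will be imputed using the baseline observation carried forward (BOCF) method".

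**The concern.** A rule that needs two significant tests is harder to meet than either test alone. Power for the pair can never exceed power for one side, and equals it only if the two sides always agree. SAP 2.7 does not mention the two-sided requirement of the decision rule, gives no correlation between sides, and does not mark its 90% as per side. Someone who reads SAP 2.7 beside SAP 2.4.3 could take 22 evaluable subjects as enough for 90% power to judge 8 mL effective, which they are not. If the group had been sized on that figure, the trial would carry a larger risk of missing its main effectiveness criterion than the SAP states.

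**Working it through.** **Inputs.** Mean change -0.74, SD 1, one-sided 2.5%, 15% drop-out and 60 planned (all SAP 2.7); one-sample t-test on each side, both required (SAP 2.4.3); BOCF for missing values (SAP 2.4.2). The correlation ρ between sides is not in the documents and is assumed to lie between 0 and 0.9.

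**Step 1: the SAP's own figure.** For one side, power = 1 − F(t₀.₉₇₅,ₙ₋₁), where F is the noncentral t distribution function with n − 1 degrees of freedom and noncentrality 0.74·√n.

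- n = 21: noncentrality 3.39, power 89.7%
- n = 22: noncentrality 3.47, power 91.1%

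So 22 is the smallest number reaching 90% for one side, and 22/0.85 = 25.9, rounded up to 26. The reference-group figure follows the same method: 79.0% at 16, 81.7% at 17, and 17/0.85 = 20. Both statements in SAP 2.7 are therefore correct single-test calculations.

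**Step 2: both sides required.** Left and right changes were simulated as bivariate normal, each with mean -0.74 and SD 1, counting success only when both t-tests were significant (1,000,000 trials per cell).

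| Evaluable | ρ = 0 | ρ = 0.5 | ρ = 0.7 | ρ = 0.9 |
|---|---|---|---|---|
| 22 | 83.0% | 84.8% | 86.1% | 88.2% |
| 24 | 87.3% | 88.6% | 89.6% | 91.2% |
| 25 | 89.1% | 90.1% | 90.9% | 92.3% |
| 26 | 90.6% | 91.5% | 92.2% | 93.4% |
| 51 | 99.9% | 99.9% | 99.9% | 99.9% |

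The ρ = 0 column can be checked by hand: 0.9112² = 0.830 at n = 22 and 0.952² = 0.906 at n = 26. For 90% on both sides, 24 (ρ = 0.9) to 26 (ρ = 0) evaluable subjects are needed. With 15% drop-out that is 24/0.85 = 28.2, so 29 included, to 26/0.85 = 30.6, so 31 included.

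**Step 3: the size the trial uses.** 60 × 0.85 = 51 evaluable. One-side power at 51 is 99.94%. The chance of failing on at least one side is at most the sum of the two failure chances, so both-side power is at least 1 − 2 × 0.0006 = 99.88%, to the rounding of the input, at any correlation. With all 60 kept and 15% of them set to zero change under BOCF, simulation gives about 99.9%.

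**Step 4: the smallest 8 mL set that is tested.** SAP 2.4.3 repeats the test in randomized subjects only. Protocol 4.1 leaves 60 − 16 = 44 randomized to 8 mL. With BOCF at 15%, both-side power there is 98.5% (ρ = 0) to 98.8% (ρ = 0.9).

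**Step 5: sensitivity to the SD.** At 22 evaluable, 90% on both sides is reached if the SD is about 0.92 (ρ = 0) to 0.97 (ρ = 0.9) or less, rather than 1.

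**The case for a change.** The best case for a correction is this. SAP 2.7 gives 22 and 26 as the effectiveness minimum and attributes 60 to safety alone, so the effectiveness justification ought to match the effectiveness rule. It does not, and the shortfall persists across the assumed range of correlations: at ρ = 0.98 the power at 22 is still 89.9%. Nor can the SD of 1 be read as a built-in allowance for two tests, since SAP 2.7 justifies it only by the absence of averaging and medians. The repair would cost a few words.

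The facts in this stand. SAP 2.7 does not say that its power is per side, and 22 evaluable subjects would not give 90% under the SAP's rule. But SAP 2.7 attaches its 90% to one test and nowhere claims it for both sides jointly, so a label is missing rather than a sum being wrong. The gap is also small beside the roundness of the inputs: the SD was raised from the pivotal study's 0.57 to 1, and a value a few hundredths below 1 would close it. Replacement minimums would in turn rest on a correlation that the documents do not supply. Above all, no decision in the trial depends on 22 or 26.

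The protocol's own sample-size text (10.11) is not visible in the public copy, so whether it labels the figure cannot be checked.

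**Conclusion.** No change is called for, because there would be no gain. The figures of 22 evaluable and 26 included are correct for one side of the face. Read against the both-sides rule they overstate power by roughly 2 to 7 percentage points (88% to 83% against the stated 90%), or by two to four evaluable subjects, for an assumed correlation of 0.9 to 0. They are lower bounds that SAP 2.7 itself sets aside in favour of 60, where both-side power is about 99.9% at any correlation, well above the 90% stated. It stays near 98.5% even among randomized subjects alone.

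This rests on the SAP's change of -0.74, SD of 1 and 15% drop-out. It speaks only to the test that both sides improve from baseline. Whether 60 and 20 subjects serve the confidence-interval overlap criterion or the safety criterion in SAP 2.1 is a separate question, not examined here.
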